5.1.4 Randomization

Enrolled subjects will be assigned a unique Subject ID manually entered in EDC. Subject information and stratification information (ie, age) are automatically transferred to the IRT system for randomization in a 1:1:1:1:1:1 ratio into 6 treatment groups and automatically assigned a unique pack ID. The subject ID will be the subject's unique identification number for all eCRFs and associated study documentation that will be used for duration of the study. After randomization, the screening number ceases to be used and remains in the screening and enrolment log only. The list of randomization assignments is produced by the IRT service provider and approved by the sponsor or delegate prior to study start.

Randomization will be stratified by age (cohorts of 6 months through <36 months, and 3 years through <9 years) and by site. The age cohorts will be of equal size. Once an age cohort attains its planned size (ie, half of the planned study sample size) the randomization in this age cohort will be blocked.

If for any reason, after signing the ICF/assent, the subject who is eligible and enrolled fails to be randomized, this is called a randomization failure. The reason for all randomization failures should be recorded in the screening and enrolment log and in the source document as specified in the source data agreement (SDA). The information on

subjects who are randomization failures should be kept distinct from subjects who are screen failures, as described in [section 5.1.2, Screening](#).

If for any reason, after randomization the subject fails to undergo treatment, this is an early termination and the reason should be recorded in source document as specified in the SDA. The information on these early termination subjects should be kept distinct in the source documentation from randomization failures.

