4. RANDOMIZATION AND BLINDING

4.1 Method of Group Assignment and Randomization

Approximately 420 subjects \geq 6 months and $<$ 9 years will be randomized to receive either one of 6 formulations of aH5N1 vaccine in a 1:1:1:1:1:1 allocation ratio, stratifying according to site and age cohort (6 months to $<$ 36 months and 3 years to $<$ 9 years). The number of subjects randomized will be approximately in an equal split between the age subgroups.

The subject will be randomized in the IRT/RTSM system. The subject will receive a unique Subject ID that will be used for all eCRFs and associated study documentation for the duration of the study. The list of randomization assignments is produced by the service provider and approved by the Sponsor according to the applicable Sponsor's Standard Operating Procedure (SOP).

The following 6 formulations will be used:

| Arm | Description |
|-----|----------------------------------|
| A | 1.875 μ g + 50% MF59 0.25 mL |
| B | 3.75 μ g + 50% MF59 0.25 mL |
| C | 7.5 μ g + 50% MF59 0.25 mL |
| D | 1.875 μ g + 100% MF59 0.5 mL |
| E | 3.75 μ g + 100% MF59 0.5 mL |
| F | 7.5 μ g + 100% MF59 0.5 mL |

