4.1.1 Definition of Randomization/Vaccination Errors

The list below provides categories for errors that may occur during vaccination.

Randomization errors:

- Administered wrong kit (Subject was vaccinated with a vaccine different from the one assigned at randomization).

Statistical Analysis Plan, Protocol Number V87_30

06 MAY 2022 Final Version 1.0

Vaccination errors:

- Administered only part of the study vaccine.
- Incorrect vaccine administration
- Administered expired vaccine.
- Administered temperature deviated vaccine.

Stratification error:

- Subject randomized in the wrong stratification stratum.

Randomization and Vaccination errors are considered as major (Clinical Study Report (CSR)-reportable) protocol deviations. Stratification error will not be considered as CSR-reportable protocol deviations (PDs) as there will no impact on the actual formulation administered. Subjects will be included in analysis according to actual age subgroup.

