8. GENERAL ISSUES FOR STATISTICAL ANALYSES

8.1 Adjustment for Covariates

The main statistical analysis includes descriptive statistics for the overall population <9 years of age. Subgroup analyses will be done by age cohort (6 months to < 36 months, 3 to < 9 years). Summary tables will show unadjusted GMTs for each vaccine group by assessment.

Adjusted GMTs will be calculated based on the log-transformed antibody titers at Day 22 and Day 43 using an Analysis of Covariance (ANCOVA) model which includes the log-transformed pre-vaccination antibody titer, age cohort and vaccine group.

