8.5 Subgroups

All analyses (safety and immunogenicity) will be done by the age cohorts (6 months to < 36 months or 3 to < 9 years). Descriptive immunogenicity analysis of the GMTs will be performed by stratifying for the following subgroups:

- Sex;
- Country;
- Site.

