The analysis model for the GMT will be done using a general linear model on log-transformed (base 10) Day 22 or Day 43 titers as the outcome variable and as covariates: formulation, log-transformed pre-vaccination titer and age subgroup. From this model, adjusted differences in the least square means (on the log scale) will be produced with 95% confidence limits for each formulation versus the standard formulation F with highest dose. The estimated difference and the confidence limits will be back-transformed to obtain an *adjusted GMT ratio* with 95% confidence limits.

Potential interaction between age stratum and treatment effect will be examined by including an interaction term in the model and present the results of the overall interaction test. The analysis will also be done for each age subgroup separately.

Geometric Mean Ratios (GMRs)

Summary statistics (geometric mean, Coefficient of variation, minimum, median, maximum) of the relative increase in titers will be presented by assessment (Day 22 and Day 43) and vaccine group overall and by age subgroup.

The analysis model for the GMR in titers will be done using the same models as mentioned on log-transformed (base 10) (Day 22 titers/Day 1 titers and Day 43 titers/Day 1 titers) as the outcome variable excluding the pre-vaccination titer as covariate.

Analysis of binary endpoints

The number and proportion of subjects achieving the binary endpoints (seroconversion or titer \geq 1: 40) will be summarized by assessment (Day 22 and Day 43) and vaccine group overall and by age subgroup. These summaries will be reported together with the associated two-sided 95% confidence intervals for the proportion according to Clopper-Pearson.

Statistical Analysis Plan, Protocol Number V87_30

06 MAY 2022 Final Version 1.0

The binary endpoints (i.e. percentage of subjects with seroconversion or with titer $\geq 1:40$) will be compared between each of formulations versus formulation F (highest dose) expressed by the differences of proportions with 95% CI using the Miettinen and Nurminen method without adjustment for the age stratum.

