11.3 Secondary Objectives Analysis

The secondary endpoints are measures of persistence of antibody responses on Day 202 to study vaccine after primary vaccinations, as determined by the HI and MN assays against the H5N1 pandemic influenza homologous strain:

- Geometric mean titers on Day 1 and Day 202 (6 months after the second vaccination) as determined by HI and MN assays.
- Geometric mean ratios calculated as follows: Day 202/Day 1 as determined by HI and MN assays.
- Percentage of subjects achieving seroconversion on Day 202.
- Percentage of subjects with a titer of $\geq 1:40$ on Day 202.

The analysis of the secondary immunogenicity endpoints will be conducted in the same way as described for the primary immunogenicity endpoints.

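### Optional refinement: the pooled seroconversion and titre ≥1:40 differences versus formulation F leave out age cohort, although age is a randomisation stratum

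*SAP*

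**What the plan says.** Protocol 5.1.4 makes age cohort a stratum ("Randomization will be stratified by age") together with site, and SAP 4.1 agrees ("stratifying according to site and age cohort").

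SAP 11.2 compares each formulation with formulation F in two ways:

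- **Titres.** The GMT model takes "as covariates: formulation, log-transformed pre-vaccination titer and age subgroup". The GMR model is the same without the pre-vaccination titre, so age stays in.
- **Binary endpoints.** Differences in seroconversion and in titre ≥1:40 get 95% intervals "using the Miettinen and Nurminen method without adjustment for the age stratum". No reason is given.

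SAP 11.3 carries this to Day 202: "The analysis of the secondary immunogenicity endpoints will be conducted in the same way as described for the primary immunogenicity endpoints".

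Two provisions limit the point. SAP 8.5 plans by-cohort results ("All analyses (safety and immunogenicity) will be done by the age cohorts"). The one-arm summaries are unadjusted by design: SAP 8.1 says "Summary tables will show unadjusted GMTs for each vaccine group by assessment", and SAP 11.2 gives each arm's percentage a Clopper-Pearson interval. Those one-arm summaries are not in question here.

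**The concern.** Among the comparisons between formulations in SAP 11.2, only the pooled binary differences leave age out. When response depends on age, an analysis that ignores the stratum counts between-cohort variation as noise, so the interval is wider than the design requires. Stratified allocation balances age among randomised children but not among those who remain in the per-protocol set. If exclusions fall unevenly by age, the crude difference mixes a formulation effect with a difference in age mix.

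Up to 5 formulations × 2 assays × 2 endpoints × 3 visits = 60 pooled differences use the method. They matter because they are the most precise binary comparisons with F that the study offers, and the by-cohort results have half the sample.

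**Working it through.** **Sample sizes (SAP 5).** 420 randomised with up to 14% excluded gives 420 × 0.86 = 361.2 evaluable. That is 361.2/2 = 180.6 per cohort, 361.2/6 = 60.2 per arm and 361.2/12 = 30.1 per arm and cohort, which reproduces the plan's 180, 60 and 30. The plan states no precision for the binary endpoints.

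**Why the pooled comparison matters.** The Wald half-width is 1.96 × √(2p(1−p)/n). For p = 0.5 and 0.8 this is 17.9 and 14.3 points at n = 60, against 25.3 and 20.2 points at n = 30. This shows the benefit of pooling, not of stratifying.

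**Large-sample effect of ignoring age.** With equal cells, the ratio of crude to stratified standard error is √[p̄(1−p̄) / mean of p(1−p)]:

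- 55/65%: √(0.24/0.2375) = 1.005
- 50/70%: √(0.24/0.23) = 1.022
- 50/80%: √(0.2275/0.205) = 1.053
- 40/80%: √(0.24/0.20) = 1.095

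**Miettinen-Nurminen intervals at the planned size.** The stratified estimate is d = Σ wₖ(p₁ₖ − p₂ₖ), with wₖ proportional to n₁ₖn₂ₖ/(n₁ₖ + n₂ₖ) and summing to 1. The limits solve (d − δ)² = 1.96² Σ wₖ²Vₖ(δ). Here Vₖ is the restricted maximum-likelihood variance times N/(N−1). The crude interval is the same calculation with one stratum of 60 per arm. Each setting used 20,000 simulated trials with no true difference between arms. All rates are assumptions.

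| Rates in the two cohorts | Mean half-width, crude (points) | Mean half-width, stratified (points) | Crude/stratified | Coverage, crude vs stratified |
|---|---|---|---|---|
| 60/60% | 17.2 | 17.2 | 1.000 | |
| 80/80% | 14.46 | 14.47 | 0.999 | |
| 50/70% | 17.2 | 16.9 | 1.018 | 95.3 vs 95.0% |
| 60/80% | 16.3 | 16.0 | 1.019 | |
| 50/80% | 16.8 | 16.1 | 1.043 | 96.5 vs 95.2% |
| 40/80% | 17.3 | 16.0 | 1.080 | 96.8 vs 95.0% |
| 94/95% | 9.50 | 9.53 | 0.998 | |
| 91/97% | 9.76 | 9.83 | 0.993 | |

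At 55/65% the ratio is 1.004. With a true deficit of 15 points versus F in both cohorts, the ratios are 1.019 (50/70%), 1.044 (50/80%) and 1.084 (40/80%), rates being those in F. In every balanced run the two point estimates were identical.

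The last two rows draw on Protocol 1.1, which gives one-dose seroconversion for a different strain: 91% and 97% in the two bands under 3 years and 95% at 3 to 8 years. The 94/95% row is the nearer match to the cohorts, since 94 is the midpoint of 91 and 97. The 91/97% row contrasts two bands inside the younger cohort, so it somewhat overstates the drawback.

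**Age imbalance after exclusions.** Suppose 10 of 70 per arm are excluded at random. The younger-cohort count among the remaining 60 is hypergeometric, with variance 60 × 0.5 × 0.5 × 10/69 = 2.174. The between-arm difference D has SD √(2 × 2.174) = 2.09, and the crude difference shifts by (D/60) × age gap.

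| Age gap (points) | SD of shift (points) | Shift of 2 points or more |
|---|---|---|
| 10 | 0.3 | 0% |
| 20 | 0.7 | 0.7% |
| 30 | 1.0 | 9.0% |
| 40 | 1.4 | 22.8% |

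An unlucky example has 33/27 evaluable by cohort in one arm and 27/33 in F, with responders 26 and 13 against 24 and 20. The crude difference is 39/60 − 44/60 = −8.3 points. The two cohort differences are −10.1 and −12.5 points with equal weights, so the stratified difference is −11.3 points. Here D = 6, a split of the size behind the 0.7% entry above.

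**The case against.** The choice is prespecified in plain words, not overlooked. No decision rests on it: SAP 11.2 tests no hypothesis, Protocol 8.2 sets no success criterion, and Protocol 8.4.2.3 plans only percentages with Clopper-Pearson intervals, so the difference versus F is an SAP addition. The gain depends on assumed rates, and the only paediatric rates by age in the documents suggest a small gap and no gain. Random exclusions cause no bias on average, and 14% is the plan's upper figure. By-cohort results will show any age dependence. The crude difference equals the difference of the tabulated percentages, which suits a descriptive report. Site is also a stratum, and the titre models omit it too.

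All of this is accurate, and it keeps the point optional. It does not make the crude method the better choice. The rates in Protocol 1.1 are for another strain after one dose and cannot exclude a larger gap here. By-cohort results do not adjust the pooled interval. On site, SAP 8.3 expects about 7, so site by age would leave roughly 30/7 ≈ 4 children per arm in each cell. Stratifying by age alone is the version that matches the titre models.

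**Conclusion.** The point holds as an optional refinement. The crude interval is valid and on average slightly conservative, and no planned conclusion is undermined. If response differs between cohorts by 20 to 40 points, the pooled half-width is about 0.3 to 1.3 points (2% to 8%) larger than an age-stratified one. With no gap or very high rates there is nothing to gain, and the stratified interval is up to about 0.7% wider. Uneven exclusions typically move the crude difference by 0.3 to 1.4 points for age gaps of 10 to 40 points.

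This rests on assumed age-specific rates, on 30 evaluable per arm and cohort, and, for the shift, on exclusions at random at about 14% in every arm.

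**What to change.** In SAP 11.2, for the overall-population comparisons with F at Days 22, 43 and (through SAP 11.3) 202, specify the Miettinen-Nurminen interval stratified by actual age cohort, with Mantel-Haenszel-type weights n₁n₂/(n₁ + n₂). Actual rather than randomised cohort follows SAP 4.1.1: "Subjects will be included in analysis according to actual age subgroup". Keep the crude difference as a supportive result, because it matches the tabulated pooled percentages; with unequal cells the stratified difference will not.

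The cost is one sentence and a small programming change, with no new data and no effect on sample size. If the crude method is kept as the main analysis, one sentence saying why the binary comparisons are unadjusted while the titre models adjust for age would close the point.

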11.3 Secondary Objectives Analysis

The secondary endpoints are measures of persistence of antibody responses on Day 202 to study vaccine after primary vaccinations, as determined by the HI and MN assays against the H5N1 pandemic influenza homologous strain:

- Geometric mean titers on Day 1 and Day 202 (6 months after the second vaccination) as determined by HI and MN assays.
- Geometric mean ratios calculated as follows: Day 202/Day 1 as determined by HI and MN assays.
- Percentage of subjects achieving seroconversion on Day 202.
- Percentage of subjects with a titer of $\geq 1:40$ on Day 202.

The analysis of the secondary immunogenicity endpoints will be conducted in the same way as described for the primary immunogenicity endpoints.

11.4 Exploratory Objectives Analysis

A *post hoc* decision will be made if other measurements will be made. If adequate sera are available and depending on assay availability, antibody responses and their persistence to seasonal and/or homologous and/or heterologous pandemic influenza strains as measured by HI, MN and SRH assays may be described at Days 1, 22, 43, and 202 in the same manner as for primary and secondary immunogenicity endpoints. The results will be included in a separate report. An additional exploratory analysis will be conducted making use of the factorial design of the study and assess the impact of the different factors (dose of MF59 and amount of antigen) on the titers and their GMT. For that we use an analysis of covariance model on log transformed (base ten) Day 22 or Day 43 HI (or MN) titers as the outcome variables and terms for covariates: age cohort, dose of MF59 adjuvant, amount of antigen and Day 1 pre-vaccination HI (or MN) titer. Potential covariate interaction effects will also be examined in this model.

Statistical Analysis Plan, Protocol Number V87_30

06 MAY 2022 Final Version 1.0

12. EFFICACY ANALYSIS

Not applicable

13. SAFETY ANALYSIS

The analysis of safety assessments in this study will include summaries of the following categories of safety data collected for each subject:

- Vaccine exposure
- Solicited local and systemic AEs
- Unsolicited AEs
- Serious AEs, NOCD, AEs leading to withdrawal, and AESIs.

13.1 Analysis of Extent of Exposure

The frequencies and percentages of subjects with first and second vaccinations will be summarized overall, by vaccine group and by age group. Data will be tabulated for the Exposed Set.

13.1.1 Safety Completeness

Analysis Solicited Adverse Events

The safety completeness analysis on solicited AEs aims to identify subjects who completed the Subject Diary Cards.

Summaries will be produced:

1. The frequencies of subjects who provided data on the diary cards by vaccine group for any vaccination and by first and second vaccination separately.

Statistical Analysis Plan, Protocol Number V87_30

06 MAY 2022 Final Version 1.0

2. For each solicited AE – including use of antipyretics/analgesics, frequency of the number of days with valid data on the diary by vaccine group for any vaccination and by first and second vaccination separately.

For the corresponding percentages, the denominator will be the respective numbers of exposed subjects. All analyses will be based on the ‘as treated’ analysis set.

13.2 Solicited Local and Systemic Adverse Events

Different diary cards have been used for subjects <3 years and subjects >=3 years.

Each solicited AE is to be assessed for 7 days following each vaccination according to a defined severity grading scale; see specifics of the solicited event and grading system below in Table 3.

Table 3 Severity Grading for Solicited Local and Systemic Adverse Events

| Age group | Type | Solicited Event | Any Event | | |
|------------|-----------------|-----------------------------------|--|---|---|
| | | | Grade 1/Mild | Grade 2/Moderate | Grade 3/Severe |
| Overall | Local | Injection site tenderness or pain | No interference with daily activity | Interferes with daily activity | Prevents daily activity |
| | | Ecchymosis | 11-25 mm | 26-50 mm | >50 mm |
| | | Erythema | 11-25 mm | 26-50 mm | >50 mm |
| | | Induration | 11-25 mm | 26-50 mm | >50 mm |
| < 3 years | Systemic | Change of eating habits | Eating less than normal for 1 - 2 feeds / meals | Missed 1 or 2 feeds / meals | Missed more than 2 feeds /meals |
| >= 3 years | | Loss of appetite | Eating less than usual with no effect on normal activity | Eating less than usual /interfered with normal activity | Not eating at all |
| Overall | | Vomiting | 1 - 2 times in 24 hours | 3 - 5 times in 24 hours | 6 or more times in 24 hours or requires intravenous hydration |

Statistical Analysis Plan, Protocol Number V87_30

06 MAY 2022 Final Version 1.0

| Age group | Type | Solicited Event | Any Event | | |
|------------------|-------------|------------------------|---|--------------------------------|--|
| | | | Grade 1/Mild | Grade 2/Moderate | Grade 3/Severe |
| Overall | | Diarrhea | 2-3 loose stools in 24 hours | 4-5 loose stools in 24 hours | 6 or more loose stools in 24 hours or requires intravenous hydration |
| < 3 years | | Irritability | Requires more cuddling and is less playful than usual | More difficult to settle | Unable to console |
| < 3 years | | Sleepiness | Shows an increased drowsiness | Sleeps through feeds / meals | Sleeps most of the time and it is hard to arouse him / her |
| >= 3 years | | Nausea | No interference with daily activity | Interferes with daily activity | Prevents daily activity |
| | | Fatigue | No interference with daily activity | Interferes with daily activity | Prevents daily activity |
| | | Myalgia | No interference with daily activity | Interferes with daily activity | Prevents daily activity |
| | | Arthralgia | No interference with daily activity | Interferes with daily activity | Prevents daily activity |
| | | Headache | No interference with daily activity | Interferes with daily activity | Prevents daily activity |
| | | Malaise | No interference with daily activity | Interferes with daily activity | Prevents daily activity |
| Overall | | Shivering/Chills | No interference with daily activity | Interferes with daily activity | Prevents daily activity |
| Overall | | Fever | 38.0 - 38.9 °C | 39 – 39.9 °C | ≥40.0 °C |

Note: presence of an event on a day is defined as mild, moderate or severe; absence is defined as none. Ecchymosis, Erythema and Induration: grading will be derived from the actual measurements in mm; Fever will be derived from the actual measured body temperature.

Statistical Analysis Plan, Protocol Number V87_30

06 MAY 2022 Final Version 1.0

Other Indicators of Reactogenicity

The use of analgesics/antipyretics will be captured as “absent” or “present” separately by reason “for treatment” or “for prevention”.

The analyses will encompass various summaries of the data by vaccination and – where applicable - combined across the two vaccinations using the solicited safety set:

1. Overall summary of subjects with solicited AEs
2. Solicited local AEs, maximum event severity by event and interval
3. Solicited systemic AEs, maximum event severity by event and interval
4. Number of days of solicited AEs, including ongoing AE after Day 7
5. Daily reports of subjects with solicited AEs, only per vaccination
6. Day of first onset of solicited AEs, only per vaccination
7. Solicited AEs ongoing at Day 7
8. Distribution of maximum temperature
9. Other use of analgesics/antipyretics

For each of the time points or time intervals presented in the summaries, only subjects with at least one valid observation (i.e., any non-missing values but excluding “Not done/unknown” and implausible values) for the solicited adverse events in the interval of interest will be considered. Subjects without valid data will be removed from the denominator to prevent a downward bias (towards zero).

All tables are run by age stratum and vaccine group. The local solicited AEs and the common systemic solicited AEs (as defined in Table 3) are also presented combining the two age strata.

Overall summary of subjects with solicited adverse events.

Any solicited AE presence is defined as at least one day recorded a presence of a local or a systemic AE. No solicited AE is defined as for all days ‘No’ for all pre-defined solicited AEs. Same convention is used considering local and systemic events separate.

The use of analgesics/antipyretics will be considered as a separate category under “other”.

Solicited local adverse events, maximum event severity by event and interval

The **maximum event severity** will be defined if there is at least one plausible non- missing observation (excluding “Not done/unknown” and implausible values) within this time interval.

Statistical Analysis Plan, Protocol Number V87_30

06 MAY 2022 Final Version 1.0

Each subject's data will be aggregated across the time points of the interval and summarized according to the maximal severity observed for each local AE, followed by a summary across subjects for each vaccine. Subjects without any solicited AEs in the interval, i.e., missing values at each of the requested time points, will be removed from the denominator.

The time intervals will be 30 minutes, Day 1 to Day 7, Day 1 to Day 3 and Day 4 to Day 7. A summary tables will be created with the frequency using only any and severe events.

Solicited systemic adverse events, maximum event severity by event and interval

The analysis on the maximum severity of the systemic adverse events will be done along the same methods as for the local adverse events.

Number of days with solicited adverse events

The number of days with the AE is defined irrespective of severity. If a solicited AE continues beyond day 7 the period after day 7 is added.

The frequency distribution of the number of days will be provided in a summary table by vaccine and by AE.

Daily reports of solicited adverse event

For each of the time points only subjects with at least one plausible observation (i.e., any non-missing values but excluding "Not done/unknown" and implausible values) for the solicited AE in the interval of interest will be considered. Subjects without plausible data (i.e. missing values or reported as "Not done/unknown" and implausible values) will be removed from the denominator to prevent a downward bias (towards zero). Data collected will be summarized (frequencies and percentages of subjects) by vaccine group, solicited AE, vaccination number and time point.

Time of first onset of solicited adverse events

The **time of first onset** is defined, for each subject, for each solicited AE, as the time point at which the respective solicited AE first occurred. The summary will provide the frequencies and percentages of subjects with first onset of each solicited AEs by vaccine group and by each time point.

For each vaccination the first onset of the AE will be used for each subject.

Statistical Analysis Plan, Protocol Number V87_30

06 MAY 2022 Final Version 1.0

For any vaccination the worst AE across all vaccinations per time point will be used. Note, ‘not done’ is treated identical to ‘missing’.

Solicited adverse events ongoing at Day 7

For each of the solicited AEs, the number of subjects reported the event ongoing at Day 7 will be summarized.

Distribution of maximum temperature

Body temperature will be summarized by 0.5 °C increments from 36.0 °C up to ≥ 40 °C by frequency tables.

Other use of analgesics/antipyretics

The use of antipyretics and analgesics will be summarized by type of use (prophylactic versus treatment) as the number and percentage of subjects reporting use.

